## Adverse Event Reporting

An adverse event is defined as “any untoward medical occurrence associated with the use of a drug in humans, whether or not considered drug related.”

A serious adverse event is defined as an adverse event “if, in the view of the investigator, it results in any of the following outcomes: Death, a life-threatening adverse event, inpatient hospitalization or prolongation of existing hospitalization, a persistent or significant incapacity or substantial disruption of the ability to conduct normal life functions, or a congenital anomaly/birth defect. Important medical events that may not result in death, be life-threatening, or require hospitalization may be considered serious when, based upon appropriate medical judgment, they may jeopardize the patient or subject and may require medical or surgical intervention to prevent one of the outcomes listed in this definition. Examples of such medical events include allergic bronchospasm requiring intensive treatment in an emergency room or at home, blood dyscrasias or convulsions that do not result in inpatient hospitalization, or the development of drug dependency or drug abuse.”

Adverse events that meet criteria for reporting will be submitted to the FDA and/or IRB as applicable. Given this high-risk patient population, a number of adverse events are expected. The key monitoring function will be to assess whether evidence is accruing that suggests a differential adverse event rate associated with treatment. AE's collected include elevated met hemoglobin or nitrogen dioxide, rebound pulmonary hypertension after discontinuing iNO, myocardial dysfunction/heart failure, hypotension, pulmonary hemorrhage, pneumothorax, PDA (if treated), NEC (stage 2b or 3), culture proven sepsis (treated with antibiotics  $\geq$  5 days), IVH (grade III or IV), ROP (severe), death, cardiac arrest or other life-threatening events. These adverse events will be collected from the time the subject starts intervention or placebo through the end of study participation (at 36 weeks corrected gestational age) and will be documented in the subject's chart.

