### **Data Collection:**

Demographic and clinical data will be prospectively collected from maternal and neonatal charts along with data from serial echocardiograms. Following variables will be included in the database

- **Maternal Data:** Age, ethnicity, educational level, smoking, alcohol or illicit use of drugs, medication history, any medical or surgical problem, antenatal screening lab results (GBS, HIV, HBs Ag, RPR) maternal UTI, chorioamnionitis, rupture of membrane, vaginal bleeding or discharge, antenatal antibiotics, steroids, indomethacin or magnesium.
- **Neonatal Data: BPD our primary outcome is determined based on the need for positive pressure ventilation or supplemental oxygen after room air challenge test**  
Gestation, Gender, mode of delivery, Apgar scores, IUGR, Birth Weight, Surfactant, Ventilation, pulmonary hypertension (early, intermittent or late), use of supplemental oxygen, culture proven infections, blood transfusions, Cardiotropic medication, bicarb infusion, saline boluses, use of indomethacin, PDA treatment/ ligation, use of diuretics, use of postnatal steroids, IVH, PVL, Post IVH hydrocephalus, NEC, ROP, ROP requiring treatment, VP shunt, Tracheostomy, Gastrostomy tube, home oxygen, home ventilation, length of hospital stay and death.

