## Study Outcome Measures (Endpoints)

- Maternal demographics (listed under the data collection section of the protocol)
- Infant measures (listed under the data collection section of the protocol)

Current Version Date:	9/10/2020	IRBNet #: 1170748
Previous Version Date:		Page 14 of 25

- Incidence of death or BPD measured at 36 weeks post menstrual age (yes or no)
  - BPD will be defined as need for supplemental oxygen for at least 28 days. Severity of BPD will be determined at 36 weeks postmenstrual age. Infants with no need for supplemental oxygen will be classified as mild BPD. Continued requirement for supplemental oxygen (<0.3 FiO2) will be considered moderate BPD. Infants requiring >0.3 FiO2 and or positive pressure respiratory support will be diagnosed with severe BPD. The need for continuing oxygen therapy will be determined by a room air challenge. We will prospectively collect data that will allow us to define BPD as recommended by the 2018 NICHD report
- Pulmonary arterial pressure based on serial echocardiograms)
- Oxygen saturation level (average for each 24-hour period after enrollment)
- Arterial pressure and oxygen saturation will be measured up to 2-weeks or until the treatment is discontinued, whichever is shorter.

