All SAEs should be reported to the PI and study Coordinator within 48 hours. Deaths should be reported to the PI and study Coordinator within 24 hours. The medical monitor will then be notified and will review the event. After review, additional notifications will be made to the DSMB, IRB, and FDA as necessary. When deemed necessary by the medical monitor, the DSMB will be notified of any significant events immediately and a meeting will take place to determine appropriate actions.

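### Read literally, the five-day antibiotic condition leaves fatal early sepsis out of the sepsis adverse event count and can bias that one line between arms

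*Combined protocol and SAP*

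**What the plan says.** The list of collected events in Adverse Event Reporting includes "NEC (stage 2b or 3), culture proven sepsis (treated with antibiotics", and the threshold of at least 5 days follows directly after those words. The sentence then continues: "5 days), IVH (grade III or IV), ROP (severe), death, cardiac arrest or other life-threatening events". Death and life-threatening events therefore stand in the same list with no duration condition. The section opens with a general definition that has no threshold either: "any untoward medical occurrence associated with the use of a drug in humans, whether or not considered drug related". It states the purpose of the list: "The key monitoring function will be to assess whether evidence is accruing that suggests a differential adverse event rate associated with treatment". It also sets the window: "These adverse events will be collected from the time the subject starts intervention or placebo through the end of study participation", that is, to 36 weeks corrected gestational age.

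Three other places bear on the point:

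- The neonatal variables under Data Collection include "culture proven infections" with no minimum length of treatment.
- The reporting paragraph after the causality table says: "Deaths should be reported to the PI and study Coordinator within 24 hours". Study Outcome Measures lists "Incidence of death or BPD measured at 36 weeks post menstrual age (yes or no").
- In the severity grading table, grade 5 covers deaths directly related to iNO toxicity. Deaths explained by the existing clinical status are left out, and sepsis is the first example given.

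**The concern.** A duration condition on treatment makes case status depend on what happens after onset. A septic infant who lives long enough can complete 5 days of antibiotics; one who dies on day 2 cannot. The cases removed are the fatal ones, and they are removed because of their outcome.

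The stated use of the list is to detect a difference in event rates between arms. If early septic deaths were more frequent in one arm, that arm's sepsis rate would be pushed down relative to the other. The death would appear on its own line, but nothing in the plan requires it to be attributed to sepsis, and the grade 5 wording keeps a death explained by sepsis out of that grade. Someone reading only the sepsis line would be misled about its direction.

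**Working it through.** **No figure to reproduce.** The plan states no sepsis rate, no sepsis hypothesis or test, and no stopping boundary based on sepsis. The check is a count under the literal rule.

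**Inputs**

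- Infants per arm: 34 (Study Site(s)/Location(s) and Number of Subjects; Sample Size Determination).
- S, infants per arm with treated culture-proven sepsis: not in the documents. Assumed to be 6, 8 or 10, equal in both arms.
- D, those among S who die before 5 days of antibiotics: not in the documents. Assumed to be 0 to 4.

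**Formulas**

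- Sepsis rate under the literal rule = (S − D)/34.
- Sepsis rate if early fatal cases also count = S/34.
- With equal S, the false advantage of arm A on the sepsis item = (D_A − D_B)/34.

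**One case:** 1/34 = 2.9 percentage points.

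**Illustrations with S = 8 in both arms** (8/34 = 23.5% when early fatal cases count)

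| Early septic deaths, A v B | Literal rule, A | Literal rule, B | False advantage of A on sepsis | Excess of A on the death item |
|---|---|---|---|---|
| 1 v 0 | 7/34 = 20.6% | 8/34 = 23.5% | 1/34 = 2.9 points | 2.9 points |
| 2 v 0 | 6/34 = 17.6% | 8/34 = 23.5% | 2/34 = 5.9 points | 5.9 points |
| 4 v 1 | 4/34 = 11.8% | 7/34 = 20.6% | 3/34 = 8.8 points | 8.8 points |

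The last column takes other deaths as equal in the two arms. With S = 6 or 10 the rates change, but the false advantage does not, because it depends only on D_A − D_B. If D is equal in both arms, each arm is undercounted by the same number and the difference between them does not move. The bias therefore needs a difference in early septic deaths; a shared undercount does not produce it.

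**At the safety review.** The monitoring committee looks at 50% enrollment. If that means half of the 68 randomised infants, evenly split (an assumption), there are 17 per arm and one case moves the sepsis rate by 1/17 = 5.9 points.

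**Where the infant appears instead.** Compared with a septic infant who survives and completes 5 days, the early fatal case takes one from the sepsis line and adds one to the death line. The two lines together do not fall.

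**The case against.** The strongest reply is that nothing is hidden. Death is in the same list without a duration condition, makes an event serious by definition, must be reported within 24 hours and counts in the primary endpoint. The list is introduced as inclusive, and rapidly fatal sepsis fits the category of other life-threatening events. The infection is also held in the neonatal data, and the Statistical Analysis Plan compares clinical characteristics of the two cohorts. All of this stands. A reader might infer that such an infant goes uncounted, that the infection is lost, or that the arm with more early septic deaths looks safer overall. The documents support none of these: that arm shows more deaths.

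A second reply is that the 5-day condition may describe an intended course, as distinct from a short rule-out course. That reading is possible, and the text does not settle it. The literal reading is equally available to whoever codes the event, so the ambiguity is itself a reason to add a clause.

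A third reply is that no stated decision rests on the sepsis count. The criteria for pausing enrollment use related serious events and safety discontinuations. That stands, and it limits the importance of the point.

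A reader might also think that the adverse event count and the neonatal infection count ought to agree. They need not. NEC, IVH and ROP are likewise recorded broadly in the database and more narrowly as adverse events, so the pattern is consistent.

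What survives is narrow. No rule says that an early fatal case will be labelled sepsis, and the one line that carries that name can drop it.

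**Conclusion.** The point holds for the sepsis item alone. On the literal wording, that item understates fatal early sepsis, by 2.9 percentage points per infant in an arm of 34. It is biased between arms only if early septic deaths differ. For a net difference of 1 to 3 such deaths, the false advantage is 2.9 to 8.8 points. These differences are assumed for illustration; the documents give neither a sepsis rate nor an early death rate. The result also rests on reading the 5-day condition as treatment actually given.

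Overall safety, alpha, power and the primary analysis are unaffected. This is a minor point of event definition.

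**What to change.** In Adverse Event Reporting, extend the sepsis item by one clause. It should count culture-proven sepsis with antibiotics for at least 5 days, or with antibiotics up to the time of death when death occurred before 5 days. The clause also settles, for infants who die early, whether the course has to be completed.

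Leave the infection variable under Data Collection as it is. Applying the 5-day rule there would narrow the only unrestricted infection count in the trial and drop survivors with shorter courses.

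The change concerns how events are counted, not how infants are treated. Infections and deaths are already collected, so the cost is the wording. The downside is that an occasional contaminant culture in an infant who dies early may be counted as sepsis.

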### Serious Adverse Events (SAE) and Adverse Events related to iNO Treatment:

Severe adverse events of special interest include one or any combination of the following

1. Pulmonary edema due to worsening of left ventricular dysfunction (occur when infants with pre-existing LV dysfunction are treated with iNO)

---

Current Version 9/10/2020 IRBNet #: 1170748  
Date:

Previous Version Page 19 of 25  
Date:

2. Elevated met Hb level (>5%) on 2 samples 6 hours apart or > 7.5% on a single reading
3. If nitrogen di-oxide (NO2) concentration is more than 3 ppm for 6 hours or more than 5 ppm on a single reading

Methemoglobinemia and elevated NO2 levels are dose dependent adverse events seen among infant treated with higher dose (>20ppm)

Adverse Events of Special Interest related to iNO treatment will be defined as one or any combination of the following

1. Rebound Pulmonary Hypertension Syndrome: This is seen after the abrupt withdrawal of iNO. Signs and symptoms of Rebound Pulmonary Hypertension Syndrome include hypoxemia, systemic hypotension, bradycardia, and decreased cardiac output. If Rebound Pulmonary Hypertension occurs, reinstate iNO therapy immediately.
2. Other rare adverse events may include thrombocytopenia (Platelets <50,000), hypokalemia (< 2.5 mEq/dl), hyperbilirubinemia while on study intervention (at phototherapy threshold for age and gestation) in absence of other known risk factors, atelectasis while on study intervention (as noted on chest x ray with lung collapse) and hypotension (below 5th centile for age and gestation)

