## Study Visits:

[figure not shown]
Infants with early pulmonary hypertension will be randomized to the treatment group or the placebo group (see randomization plan). iNO or placebo treatment will start at 20 ppm. Treatment will continue for 2 weeks or until resolution of pulmonary hypertension, whichever comes first.

Current Version	9/10/2020	IRBNet #: 1170748
Date:		
Previous Version		Page 12 of 25
Date:		

To ensure the safety and evaluate the clinical response to iNO treatment, we will perform serial echocardiograms as shown in figure 2.

Figure 2

Time Line for Serial Echocardiography

\*PMA: Post Menstrual Age  
+ PH: Pulmonary Hypertension

Since the data of SpO2 & FiO2 are available in all infants, their ratios (SF ratio) will be calculated as markers of improved oxygenation. SF ratio has the advantage of avoiding invasive arterial blood sampling in situation when umbilical arterial line is unavailable. It is a reliable noninvasive surrogate for PaO2: FiO2 ratio to identify children with severe lung disease. Respiratory Severity Score (RSS= FiO2 X Mean airway pressure (MAP)) will be monitored for infants on mechanical ventilation since the data of mean airway pressure will be available. Significant response to iNO treatment will be defined as 20% improvement in SF ratio or resolution of pulmonary hypertension (assessed by echo) within 72 hours. Serial echocardiograms will be performed every 24-48 ± 12 hours until 14 days of life irrespective of the length of treatment.

Current Version 9/10/2020  
Date:

IRBNet #: 1170748

Previous Version  
Date:

Page 13 of 25

If PH is resolved during the 2-week treatment window or after the completion of the 2-week treatment protocol, we will start weaning the iNO dose by decreasing to 15 ppm. Weaning will continue to 10, 5, 4, 3, 2 and 1 ppm every 4 hours. During the weaning process if SF ratio decreased by 20%, iNO /Placebo dose will be increased to the minimum dose where  $\text{FiO}_2$  and  $\text{PaO}_2$  were stable. Weaning can be resumed after 12 hours following the above guidelines. The iNO weaning process described above is the current standard of care in our NICU for infants with PH. If pulmonary hypertension recurs in the first 2 weeks of life after stopping the treatment, iNO/Placebo treatment will be resumed based upon the randomization at the time of enrollment.

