### Mitigation of Risks:

We will measure levels of methemoglobin with blood gases as is current standard of care in the NICU. The first methemoglobin level will be checked within 4-8 hours of treatment initiation, and then repeated every 24-48 hours during the intervention. Methemoglobinemia can be reversed by stopping the iNO.

Our device has an alarm set at 0.7ppm for live monitoring of NO2 that is set well below the threshold for any adverse effect.

Study team will seek clearance from the clinical team before performing echocardiogram to ensure the safety of the infant. If an infant is clinically unstable, study echocardiogram can be delayed or cancelled

During the course of study, the attending clinicians may request unmasking of intervention (iNO or placebo) only if oxygenation index is higher than 40 for at least 4 hours or if there is risk of

---

Current Version 9/10/2020 IRBNet #: 1170748  
Date:

Previous Version Page 17 of 25  
Date:

death due to hypoxic respiratory failure without starting iNO. If the infant is on iNO, treatment will continue. If the infant is on placebo, iNO treatment may be allowed. The PI will be notified immediately. A protocol violation will be filed and intention to treat principle will apply.

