## Early Withdrawal of Subjects

### Investigator Withdrawal of Subjects

- A. The following stopping criteria will be followed: Patient experiences a serious adverse event (defined per regulation) related to study drug
- B. Patient experiences any one of the following:
  - I. Pulmonary edema due to worsening of left ventricular dysfunction
  - II. Elevated met Hb level (>5%) on 2 samples 6 hours apart or > 7.5% on a single reading
  - III. If nitrogen di-oxide (NO2) concentration is more than 3 ppm for 6 hours or more than 5 ppm on a single reading
- C. Investigator judgement

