## Criteria for Cessation of Enrollment Pending DSMB Review of Safety Data

1. Two or more infants experience an SAE related to iNO treatment
2. Two or more infants are discontinued from the study due to safety concerns

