## Data Collection and Follow-up for Withdrawn Subjects

Subjects who are withdrawn from the study will not be included in the final analysis. All AEs and SAEs will continue to be collected on withdrawn subjects throughout hospitalization, and that data will be reviewed by the DSMB when necessary.

---

Current Version 9/10/2020 IRBNet #: 1170748  
Date:

Previous Version Page 18 of 25  
Date:

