#### **Severity Grading School for Adverse Events:**

Adverse event severity will be graded as below

Classification	Examples
Mild (Grade 1) infants are asymptomatic or have mild symptoms associated with study intervention that require clinical or diagnostic observations only; no intervention indicated.	
 
• Methemoglobinemia >2%
 
• NO2 > 1.5
 
• Hypokalemia <3
 
• Left Ventricular Dysfunction: Ejection Fraction decrease by 20%
 
• Thrombocytopenia: Platelets <100,000
 
• Hyperbilirubinemia in the absence of other known risk factors that requires single phototherapy
 
• Mild Hypotension (mean BP < # gestation weeks) that requires no treatment
 

Moderate (Grade 2) if infants have moderate symptoms that require discontinuing study intervention, non-urgent treatment or intervention	
 
• Methemoglobinemia >3%
 
• NO2 > 2
 
• Hypokalemia <2.7
 
• Left Ventricular Dysfunction: Ejection Fraction decrease by 30%
 
• Thrombocytopenia: Platelets <50,000
 

Current Version 9/10/2020  
Date:

IRBNet #: 1170748

Previous Version  
Date:

Page 20 of 25

	
 
Hyperbilirubinemia in the absence of other known risk factors that requires double phototherapy
 
Moderate Hypotension (mean BP < # gestation weeks) that requires IV fluid boluses after starting intervention
 

Severe (Grade 3): Infants developed severe or medically significant symptoms that is not immediately life threatening but require treatment or intervention.	
 
Methemoglobinemia >5%
 
NO2 > 3
 
Hypokalemia <2.5
 
Left Ventricular Dysfunction: Ejection Fraction decrease by 40%
 
Thrombocytopenia: Platelets <30,000
 
Hyperbilirubinemia in the absence of other known risk factors that requires triple phototherapy
 
Severe Hypotension (mean BP < # gestation weeks) that require single cardiotropic infusion after starting the study intervention
 

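### Randomized infants whose study gas is stopped for safety can be read as withdrawn, and withdrawn infants are dropped from the final analysis

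*Combined protocol and SAP*

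**What the plan says.** All references are to the combined protocol and SAP.

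- **Investigator Withdrawal of Subjects** (under Early Withdrawal of Subjects). Criterion A reads "The following stopping criteria will be followed: Patient experiences a serious adverse event (defined per regulation) related to study drug". Criterion B lists pulmonary edema from worsening left ventricular function, and methemoglobin or nitrogen dioxide above set limits. Criterion C is investigator judgement.
- **Data Collection and Follow-up for Withdrawn Subjects.** "Subjects who are withdrawn from the study will not be included in the final analysis". The next sentence adds "All AEs and SAEs will continue to be collected on withdrawn subjects throughout hospitalization".
- **Criteria for Cessation of Enrollment Pending DSMB Review of Safety Data.** Item 2 reads "Two or more infants are discontinued from the study due to safety concerns".
- **Severity grading table.** Grade 2 applies "if infants have moderate symptoms that require discontinuing study intervention".
- **Mitigation of Risks.** After the rule on unmasking and rescue iNO: "A protocol violation will be filed and intention to treat principle will apply".
- **Rebound pulmonary hypertension.** It is listed as an adverse event of special interest related to iNO, with the instruction "If Rebound Pulmonary Hypertension occurs, reinstate iNO therapy immediately". For recurrence in the first two weeks of life, Study Visits says "iNO/Placebo treatment will be resumed based upon the randomization at the time of enrollment", with an exception for non-responders.

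The Statistical Analysis Plan section does not define an analysis set.

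**The concern.** Stopping an assigned treatment and leaving a trial are different events. An infant taken off gas for a high methemoglobin level can still be followed to 36 weeks postmenstrual age and counted for death or BPD. The protocol places its gas-stopping rules under a heading about withdrawing subjects and then removes withdrawn subjects from the analysis.

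The protocol attributes most of the listed triggers to iNO: drug-related serious events, methemoglobin, nitrogen dioxide, and pulmonary edema when iNO is given with pre-existing left ventricular dysfunction. Placebo infants should rarely meet them. The exclusion would therefore depend on treatment and fall mainly on one arm, so the arms compared would no longer be the arms randomized.

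The rule can also discard primary-outcome data already in hand. Death is on the list of collected adverse events, and adverse events continue to be collected on withdrawn infants. A later death would be recorded for safety and left out of the death-or-BPD comparison. No equivalent provision secures BPD status for these infants.

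**Working it through.** **Step 1. The rules side by side.**

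| Situation | Study gas | Analysis status as written |
|---|---|---|
| Placebo infant unmasked and given rescue iNO | Moves to iNO | Kept, intention to treat (Mitigation of Risks) |
| Methemoglobin, nitrogen dioxide or pulmonary edema limit met (criterion B) | Stopped | Dropped, if meeting the criterion is withdrawal |
| Related serious event (A) or investigator judgement (C) | Stopped | Dropped, on the same reading |
| Rebound judged serious and related | Restarted under the rebound instruction | Dropped through criterion A, on the same reading; no exemption stated |

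The reading turns on whether the criteria mean leaving the study. The section heading and DSMB item 2 ("Two or more infants are discontinued from the study due to safety concerns") say so. The list itself is introduced as stopping criteria, and the Grade 2 wording refers to the intervention. The plan uses both ideas without saying which governs the analysis.

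**Step 2. Inputs for size.** The rule rests on no figure of its own. Sample Size Determination gives 34 per arm, 80% incidence, and a 30% relative decrease.

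- iNO rate: 0.80 × (1 − 0.30) = 0.56.
- Whole infants: 0.80 × 34 = 27.2, taken as 27; 0.56 × 34 = 19.04, taken as 19.
- The 34 is taken as given. The usual two-sided formula for 80% versus 56% gives 59 per arm, a separate matter that does not bear on this point.

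**Step 3. Effect of dropping iNO infants.** RR = (iNO events / iNO n) ÷ (27/34). The p-values are Pearson chi-square without and with continuity correction, then Fisher exact.

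| iNO arm analysed | RR | Uncorrected | Corrected | Fisher |
|---|---|---|---|---|
| 19/34, all kept | 0.704 | 0.038 | 0.070 | 0.068 |
| 19/33, one dropped without the outcome | 0.725 | 0.054 | 0.096 | 0.068 |
| 18/33, one dropped with the outcome | 0.687 | 0.030 | 0.057 | 0.039 |
| 19/32, two dropped without | 0.748 | 0.077 | 0.133 | 0.109 |
| 17/32, two dropped with | 0.669 | 0.024 | 0.045 | 0.036 |

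With no treatment effect (27/34 in both arms), dropping two iNO infants gives 25/32, RR 0.98, or 27/32, RR 1.06.

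**Step 4. False-positive rate in the least favourable case.** Assume a true rate of 80% in both arms, and that every dropped iNO infant had the outcome. Exact binomial enumeration with the uncorrected chi-square puts the chance of a significant result favouring iNO at 2.6% with nobody dropped, 3.2% with one dropped and 5.1% with five dropped.

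**Step 5. How often.** The documents give no rate for any trigger. For an assumed probability q per iNO infant, the expected number dropped is 34q, and the chance of at least one is 1 − (1 − q)^34.

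| Assumed q | Expected number | Chance of at least one |
|---|---|---|
| 0.1% | 0.03 | 3% |
| 0.5% | 0.17 | 16% |
| 1% | 0.34 | 29% |
| 3% | 1.02 | 64% |
| 6% | 2.04 | 88% |

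**The case against.** **The criteria may mean stopping gas only.** They are introduced as stopping criteria, and the Grade 2 wording can support that reading. This stands as an ambiguity. It does not settle analysis status, because the section heading and DSMB item 2 point the other way.

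**Intention to treat is already stated.** It is, but only in the paragraph on unmasking and rescue iNO. A deteriorating infant at risk of death from hypoxic respiratory failure may enter that route, so some of the worst cases do have a stated rule. An infant stopped for methemoglobin or nitrogen dioxide does not enter it on those grounds. A reader might infer a direct contradiction between the two sections. The text shows a principle stated for one situation and not carried to the others.

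**The triggers should be uncommon.** The protocol calls the methemoglobin risk minimal and associates raised methemoglobin and nitrogen dioxide with doses above 20 ppm; this trial starts at 20 ppm. This stands and limits the expected size.

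**Rebound.** A reader might infer that rebound as such leads to exclusion, or that the restart rule is unsettled. The documents support neither. Rebound is not on the list of severe events of special interest. The firmest causality category requires other causes to be ruled out and/or recurrence on re-exposure, while the possibly-related category allows for underlying disease, and every randomized infant has pulmonary hypertension. Rebound is linked to abrupt withdrawal, whereas the plan weans stepwise. Restart is covered by the rebound instruction, the recurrence rule and the non-responder exception.

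**Conclusion.** The concern holds as an analysis-set fault. Read as written, the withdrawal and follow-up sections exclude randomized infants for events tied to the study drug, and nothing in the analysis plan overrides that. Rebound is one conditional route into the exclusion, not its cause.

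The expected numerical effect is small: RR 0.69 to 0.73 with one iNO infant dropped and 0.67 to 0.75 with two, against 0.70 with all kept. A reader might take the p-value changes as evidence that the trial's conclusion is at risk. They illustrate only how sensitive 34 per arm is. Any one-infant exclusion would do the same, and with one dropped the continuity-corrected p-value stays above 0.05 throughout.

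These figures assume the design rates, placebo fixed at 27/34, and exclusions only from the iNO arm. The frequency of such exclusions cannot be taken from the documents. The change should be made because the rule weakens the randomized comparison and is easily removed.

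**What to change.** 1. **Investigator Withdrawal of Subjects.** State that meeting A, B or C stops study gas only, and that the infant stays in follow-up to 36 weeks postmenstrual age.
2. **Data Collection and Follow-up for Withdrawn Subjects.** Replace the first sentence with: *Every randomized infant is included in the primary analysis in the assigned arm, including infants who stopped study gas, unless the parents withdraw consent to data use; such cases are reported by arm.*
3. **Criteria for Cessation of Enrollment, item 2.** Refer to infants who stopped study gas for safety concerns rather than infants discontinued from the study. Otherwise edit 1 would leave the DSMB trigger with little to count.

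No exemption of rebound from criterion A and no rewrite of the restart instruction is needed, since edit 2 settles analysis status on its own.

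The cost is text only, with no change to sample size, visit schedule or gas supply. The downside is that infants who stopped gas early stay in the comparison, which may slightly dilute the estimated effect.
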